9.3 EXPLORATORY ANALYSES

In addition to unadjusted pre- vs post- outcome comparisons, we will utilize additional analytic approaches to explore exposure-outcome relationships between the study DSI and ICU antimicrobial use. These will include: 1) interrupted time series analyses of rates at the calendar month level to account for changes in temporal trends antecedent to the time of the intervention, 2) individual subject-level negative binomial analyses with a covariate for admitted pre vs. post intervention date.

For the interrupted time series analysis, will treat each calendar month (beginning as the unit of analysis. Each month will have an average antibiotic DOT per mechanically-ventilated patient per day. Linear regression will be used to model change over time, as well as an interaction for the change over time before and after the start of the trial intervention date.

Subject-level analyses will also be performed to account for confounding clinical variables impacting ICU antimicrobial use. We will utilize patient-level data from pre-intervention historical control data to construct a multivariate model predictive of ICU-AURs. For these analyses, all study subjects will have a calculated rate of ICU-AURs (e.g., total antibiotic DOTs on mechanical ventilation divided by total number of person days on mechanical ventilation). Multiple imputation using fully conditional specification will be performed to create 25 imputation data sets to account for missing data, and negative binomial regression models were constructed for each data set using backwards selection. Covariates will be retained in a final multivariate master model if they are retained in 100% of negative

binomial regression models, after evaluation for multicollinearity. Admission before or after the study intervention will then be to the final model as a covariate to determine the independent effect of the study intervention on antibiotic use.

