5 STUDY DESIGN

5.1 OVERALL DESIGN

We plan to conduct a quasi-experimental, single-arm pilot/feasibility trial of a VAP diagnostic stewardship bundle in the MM Critical Care Medicine Unit (CCMU) and Cardiac Care Unit (CCU). This is a population-based rather than individual intervention. Both the CCMU and CCU will designate team leaders (one faculty member, fellow, and unit nurse), who will be instructed on study design and rationale, to disseminate study information and education in concert with study PI to colleagues through use of infographics and powerpoint-based sessions.

The study intervention will consist of interventions at all 3 phases of the diagnostic testing pathway (see Section 7 for full details). The bundle's first two interventions (ordering & collection phase interventions) will be implemented at the onset of the study period. The final bundled intervention (reporting phase) will be implemented 6 months after study onset (see Study Timeline (section 1.2)).

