9.2 ANALYSIS OF THE PRIMARY AND SECONDARY ENDPOINT(S)

Primary and secondary study outcomes will be compared between patient cohorts before and after DSI implementation. All primary/secondary study outcomes will compare patients admitted to study ICUs over the course of the year-long study intervention (Feb 2022-23) versus those admitted in the pre-intervention historical control period (Feb 2017-22). As above, rate variables will be compared using a z-score test. A p-value of 0.05 will be utilized for statistical significance.

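### The interrupted time series names only a change in slope at one date: a level term, a second change point for the reporting step and the error structure are left unspecified

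*Combined protocol and SAP*

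**What the plan says.** Section 9.3 plans an interrupted time series of antibiotic use, intended "to account for changes in temporal trends antecedent to the time of the intervention". It "will treat each calendar month (beginning as the unit of analysis", and the outcome is defined by "Each month will have an average antibiotic DOT per mechanically-ventilated patient per day". The model is described in one sentence: "Linear regression will be used to model change over time, as well as an interaction for the change over time before and after" go-live. No equation, weights, error structure or effect coefficient is given.

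Section 9.2 gives the two periods: "those admitted in the pre-intervention historical control period (Feb 2017-22") and "the year-long study intervention (Feb 2022-23"). Section 5.1 starts the ordering and collection steps together at study onset. The third step comes later: "The final bundled intervention (reporting phase) will be implemented 6 months after study onset".

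Section 9.4.2 adds subgroup comparisons by implementation phase against the same calendar months in the historical period.

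**The concern.** The model described does not match how the bundle is introduced. The ordering and collection steps are switched on in full at onset through an interruptive alert, so an abrupt change in level is a natural expectation. A model with only a slope change has to draw that step as a ramp. The reporting step starts halfway through the intervention year, and a model with one change point has nowhere to put it. Plain linear regression on consecutive months also treats them as independent and equally precise.

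What is at stake is the size and timing of the antibiotic effect after allowing for trend. The other antibiotic analyses do not make that allowance:

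- Section 9.2 compares crude rates for one year with those for five.
- The subject-level model in section 9.3 adds a before/after covariate and states no calendar trend.
- The phase subgroups in section 9.4.2 match months for seasonality only.

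Section 4 says adherence results may be used to recalibrate the bundle before multi-center use. An effect credited to the wrong step or the wrong month would mislead that decision.

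**Working it through.** The plan gives no effect size, monthly variability or power for this analysis, so there is no figure to reproduce. The check asks what each plausible model returns when the true pattern is known.

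**Inputs.** Section 9.2 gives 60 months before and 12 after (taken from the February-to-February dates). Section 5.1 puts two steps at month 0 and one after 6 months, so the reporting effect first appears in post month 7. Assumed: flat prior trend, no noise, total drop of 1.0. Results scale in proportion.

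**Models.** Let t = 1..72, D = 1 for t > 60, R = 1 for t > 66, and s = time since start (coded 0-11 or 1-12).

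- M1, literal reading: y = a + b·t + c·s·D
- M2, level added: y = a + b·t + d·D + c·s·D
- M3, two levels: y = a + b·t + d·D + r·R

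**True pattern A: drop of 1.0 at onset, sustained.**

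- M1 with s = 0-11: c = -0.1012. Month 1 is 0; month 12 is -0.1012 × 11 = -1.11; the average is -0.1012 × 5.5 = -0.56.
- M1 with s = 1-12: c = -0.0987. Month 1 is -0.10; month 12 is -0.0987 × 12 = -1.18; the average is -0.0987 × 6.5 = -0.64.
- The average is therefore understated by 36-44%, and a decline is reported where none exists.
- M2: d = -1.00 and c = 0, which is exact.

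**True pattern B: drop of 1.0 only at the reporting step** (true 12-month average -0.50).

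- M1 gives an average of -0.27 to -0.33 in months 1-6 (true 0) and about -0.90 in months 7-12 (true -1.00).
- M2 with s = 0-11: d = +0.1923 and c = -0.1259. Month 1 is +0.19; month 12 is 0.1923 - 11 × 0.1259 = -1.19; the average is 0.1923 - 5.5 × 0.1259 = -0.50. The average is right and the timing is wrong.

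**True pattern C: 0.5 at each step** (true average -0.75).

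- M2 gives -0.40 in month 1, a false slope of -0.063 per month, and an average of -0.75.

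**M3** recovers A, B and C exactly. If the truth is instead a gradual fall of 0.10 per month starting from zero in month 1, M3 gives phase averages of -0.24 and -0.84, against true values of -0.25 and -0.85.

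**Serial correlation.** The documents give no autocorrelation, so 0.2, 0.3 and 0.4 are assumed. In simulations with no true effect, ordinary least squares at nominal 5% rejected as follows:

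- M1 slope: about 10%, 14% and 18-19%.
- M2 level: about 9-10%, 13% and 16-17%.
- With no autocorrelation, both are about 5%.

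**Choice of correction.** This was simulated on a model with level and slope at onset and a second level, for autocorrelation from 0 to 0.4. Newey-West errors (lag 3, small-sample scaling) rejected a true null about 19-32% of the time, ordinary least squares 5-15%, and AR(1) generalized least squares 5-8%. Newey-West is also too liberal when the slope term is dropped.

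**The case against.** The strongest reply is that section 9.3 gives a prose outline, not an equation. A time-by-period interaction is normally fitted with the period main effect, and that main effect is the level term. A reader might infer that the plan excludes a step. The text does not say so, and with the main effect an immediate step is recovered exactly. Even a version without the main effect, using raw calendar time 1-72, averages -1.00 under pattern A, although its coefficient is -0.015 per month and has no useful reading. This part stands: the fault is that the level term is unspecified, and defensible readings give different answers.

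A reader might also infer that a one-break model reports the wrong sign. That needs the ordering and collection steps to have no effect at all. With half the effect at each step, month 1 has the right sign (-0.40). A larger wrong-sign value (+0.32) appears only if s is coded 1-12 and the line is extrapolated back to month 0. In both cases the 12-month average is correct.

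It would likewise go too far to say that the p-values will be too small. That depends on an autocorrelation the documents do not report. Section 7.2.1 describes three months of provider education during rollout, so a gradual effect is also plausible.

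Finally, the analysis is labelled exploratory and concerns antibiotic use only, and section 9.4.2 does look at the two phases. Both points limit the severity. The phase subgroups have no trend adjustment, so they do not supply what the time series leaves out.

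**Conclusion.** The concern holds as a gap in specification. The single change point is a weakness under every reading: no model with one break at onset can locate an effect that starts six months later. The missing level term matters if the sentence is followed literally with time counted from go-live; an immediate drop of 1.0 then averages 0.56 to 0.64. The error structure is also unstated. If autocorrelation were 0.2 to 0.4, the true error of a nominal 5% test would be about 10-19%.

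These sizes rest on the 60/12-month split, a flat prior trend, step-shaped effects and assumed autocorrelation. The primary safety comparisons and the main before/after antibiotic test are unaffected. The point still deserves correction, because this is the only stated analysis that separates the bundle from the prior trend and the correction is cheap.

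**What to change.** Write the equation into section 9.3:

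- A time trend, a level term at February 2022 and a second level term at the start of the reporting phase. Keep any post-intervention slope term as a sensitivity analysis, given the possible gradual uptake.
- Months weighted by ventilated patient-days.
- AR(1) errors by generalized least squares with REML. Newey-West should not be used, because it is badly anti-conservative with six months per phase.
- A statement of which coefficients represent the effect of the first two steps and the added effect of reporting.

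The cost is SAP wording and a few lines of code, with no new data. Precision is limited by six months per phase. With independent errors and a true step equal to one monthly standard deviation (an assumed size), power in the two-level model is about 52% for a step at onset and 40% for a step at the reporting phase. If a slope and a second level are both kept, the standard error of the slope change about doubles and that of the first level rises by about 7%.

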1 PROTOCOL SUMMARY

1.1 SYNOPSIS

[figure not shown]
Title:	Implementation of a Diagnostic Stewardship Bundle for Ventilator-associated Pneumonia among Mechanically-ventilated patients: a pilot/feasibility trial.
Grant Number:	Not applicable
Study Description:	A pilot/feasibility trial to evaluate the safety and efficacy of a multi-faceted ventilator-associated pneumonia diagnostic stewardship bundle. Trial ICUs will sequentially implement interventions targeting the respiratory culture diagnostic testing pathway to minimize diagnostic error and overtreatment of ventilator-associated pneumonia.
Objectives:	
Primary Objective: To determine the safety of a multi-faceted ventilator-associated pneumonia diagnostic stewardship bundle.
 
Secondary Objectives:
 
- To determine the association between a multi-faceted ventilator-associated pneumonia diagnostic stewardship bundle and ICU antibiotic utilization rates.- To determine the association between a multi-faceted ventilator-associated pneumonia diagnostic stewardship bundle and rates of positive respiratory cultures.
Endpoints:	To assess study feasibility and adherence to protocolized intervention.
	
Primary Endpoints:
 
- Mortality per 1000 mechanically-ventilated patient days- Ventilator-associated events (using Centers for Disease Control/National Healthcare Safety Network definitions) per 1000 patient days- Median duration of mechanical ventilation per patient.
	
Secondary Endpoints:
 
- Positive respiratory cultures per 1000 mechanically-ventilated patient days.- Total ICU antibiotic utilization rates (total antibiotic days of therapy per 1000 mechanically-ventilated patient days).- Broad-spectrum ICU antibiotic utilization rates (broad-spectrum antibiotic days of therapy per 1000 mechanically-ventilated patient days).- Respiratory cultures ordered per 1000 patient days.- Percentage of respiratory cultures obtained by BAL.- Percentage of respiratory cultures from BAL samples with alveolar neutrophils <50% (for Phase 2 only)
Study Population:	All mechanically-ventilated patients hospitalized within Michigan Medicine Cardiac Care Unit (CCU) and Critical Care Medicine Unit (CCMU).

Phase or Stage:	Pilot/feasibility trial of a population-based intervention.
Description of Sites/Facilities Enrolling Participants:	2 Michigan Medicine Intensive Care units.

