4 OBJECTIVES AND ENDPOINTS

OBJECTIVES	ENDPOINTS	JUSTIFICATION FOR ENDPOINTS
Primary		
To determine the safety of a multi-faceted ventilator-associated pneumonia diagnostic stewardship bundle.	
Mortality per 1000 mechanically-ventilated patient days
 
Ventilator-associated events (using Centers for Disease Control/National Healthcare Safety Network definitions) per 1000 patient days
 
Median duration of mechanical ventilation per patient.
	The goal of this study is to demonstrate preliminary safety of a diagnostic stewardship bundle for ventilator-associated pneumonia.
Secondary		
To determine the association between a multi-faceted ventilator-associated pneumonia diagnostic stewardship bundle and ICU antibiotic utilization rates.	
Total ICU antibiotic utilization rates (total antibiotic days of therapy per 1000 mechanically-ventilated patient days).
 
Broad-spectrum ICU antibiotic utilization rates (broad-spectrum antibiotic days of therapy per 1000
	Our preliminary data suggests that a bundled diagnostic stewardship intervention can successfully reduce antibiotic use in mechanically-ventilated patients.

OBJECTIVES	ENDPOINTS	JUSTIFICATION FOR ENDPOINTS
	mechanically-ventilated patient days).	
To determine the association between a multi-faceted ventilator-associated pneumonia diagnostic stewardship bundle and rates of positive respiratory cultures.	Positive respiratory cultures per 1000 mechanically-ventilated patient days.	
To assess study feasibility and adherence to protocolized intervention.	Respiratory cultures ordered per 1000 mechanically-ventilated patient days Percentage of respiratory cultures obtained by BAL Percentage of respiratory cultures from BAL samples with alveolar neutrophils <50%	Adherence to study intervention is crucial to evaluating study efficacy and potentially recalibrating approach to intervention prior to multi-center implementation.

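### Section 9.3 fits negative binomial regression to a per-patient antibiotic ratio and names no exposure offset, weight or robust variance, so its standard errors depend on the unit and its target is not the pooled endpoint

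*Combined protocol and SAP*

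**What the plan says.** Section 9.3 (Exploratory Analyses) lists "individual subject-level negative binomial analyses with a covariate for admitted pre vs. post intervention date". It then defines the outcome: "For these analyses, all study subjects will have a calculated rate of ICU-AURs", illustrated as "total antibiotic DOTs on mechanical ventilation divided by total number of person days on mechanical ventilation". After multiple imputation into 25 data sets, "negative binomial regression models were constructed for each data set using backwards selection". The pre/post indicator is added last, "to determine the independent effect of the study intervention on antibiotic use".

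Neither 9.3 nor any other section mentions an offset, an exposure variable, a weight or a robust variance estimator for this model.

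The formula in 9.3 implies a rate per ventilated day. The synopsis (1.1) and section 4 define the matching secondary endpoint on another scale, "total antibiotic days of therapy per 1000 mechanically-ventilated patient days", which is a pooled unit-level rate.

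For the interrupted time series, 9.3 says "Each month will have an average antibiotic DOT per mechanically-ventilated patient per day".

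**The concern.** Three things follow if the text is carried out as written.

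- A count likelihood is applied to a non-integer ratio. Negative binomial variance is mean + alpha × mean², which does not rescale with the response. The model-based standard error and p-value, and any backwards selection that uses them, then depend on whether the ratio is expressed per day or per 1000 days.
- Dividing by ventilated days removes exposure from the model. A ratio observed over one day counts as much as one observed over thirty.
- The quantity estimated is a contrast of mean patient ratios. The endpoint it is meant to adjust is total DOT over total ventilated days.

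The comparison in 9.2 is unadjusted and the time series models calendar time only. This is therefore the only covariate-adjusted estimate of the bundle's effect on antibiotic use, and 9.3 presents it as the independent effect.

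**Working it through.** **Inputs.** The documents give no patient numbers, ventilation times, DOT rates or expected effect, so there is no planned figure to reproduce. Section 9.2 gives five control years and one intervention year; a 5:1 patient ratio is assumed from that. All other simulation inputs below are assumptions.

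**1. Dependence on the unit.** In a two-group log-link negative binomial model, SE² = v0/n0 + v1/n1, where v = 1/mean + alpha and both terms are in the chosen unit. In a simulated data set of 5,000 + 1,000 patients:

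- Per day: estimate −0.1032, fitted alpha 0.0007. Take a control mean of 1.2 DOT/day; the intervention mean is 1.2 × exp(−0.1032) = 1.082. Then v0 = 0.834, v1 = 0.925, and SE = √(0.834/5000 + 0.925/1000) = 0.033, p = 0.0018.
- Per 1000 days: estimate −0.1006, fitted alpha 1.823. The 1/mean term is about 1/1200 = 0.0008, so v ≈ 1.824 and SE = √(1.824 × (1/5000 + 1/1000)) = 0.047, p = 0.032.

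The estimate barely moves, but the standard error rises by about 40%. Over 18 further assumption sets (1,000 + 200 or 2,500 + 500 patients; 0.8 to 1.6 DOT/day) the per-1000 SE was 1.02 to 1.60 times the per-day SE. The p-value crossed 0.05 in three of them: 0.028 against 0.102, 0.0046 against 0.063, and 0.026 against 0.151.

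A separate simulation (4,000 + 800 patients, median ventilation 3 days, log-SD 1.0, about 1.4 DOT/day, frailty 0.3, 60 trials) gave log rate ratio −0.074. Its SE was 0.034 per day (z = 2.2, p = 0.03) and 0.045 per 1000 days (z = 1.6, p = 0.10), against a true 0.031.

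Type I error with model-based SE (400 null runs, 1,000 + 200 patients) was 0.037 per day, 0.000 per 1000 days and 0.048 for count plus offset.

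**2. Weight per patient.** The information weight is mu/(1 + alpha × mu). With the ratio as response, mu does not contain ventilated days, so the 30-day to 1-day weight ratio is 1.0. With a log(days) offset, mu = 1.2 × days. At alpha 0.25 the ratio is [36/(1 + 9)] ÷ [1.2/(1 + 0.3)] = 3.9; at alpha 0.5 it is 2.5, at alpha 1 it is 1.8, and it reaches 30 only in the Poisson limit.

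**3. Mean of ratios against pooled rate.** Take a 1-day patient with 3 DOT and a 30-day patient with 15 DOT. The mean of ratios is (3 + 0.5)/2 = 1.75; the pooled rate is 18/31 = 0.58. Whether the intervention contrast also differs depends on the pattern of effect. In the simulations the distribution of ventilated days was the same in both periods:

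| Assumed effect | NB on ratio | NB, count + offset | Pooled |
|---|---|---|---|
| 20% reduction from ventilator day 3 on (median 3 days) | 0.93 | 0.91 | 0.88 |
| Rate ratio 0.70 only in stays of 5 days or more | 0.871 | 0.829 | 0.780 |
| Constant 20% reduction | 0.80 | 0.80 | 0.80 |

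With a median of 5 days, the day-3 setting gave 0.90–0.91 for the ratio model against 0.85–0.86 pooled.

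**4. After the change.** With a count response and offset, the p-value was the same for exposure in days or thousands of days. Negative binomial with offset closes (0.93 − 0.91)/(0.93 − 0.88) = 40% of the gap to the pooled endpoint in the first row and (0.871 − 0.829)/(0.871 − 0.780) = 46% in the second. Quasi-Poisson with only the period indicator and the offset returns total DOT over total days in each period, so it matches the endpoint.

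**The case against.** The strongest reply is that 9.3 is silent on an offset and does not exclude one. It names numerator and denominator only by way of example, and an analyst who speaks of modelling a rate by negative binomial regression often means a count with a log-exposure offset. That is possible, but the text makes the ratio itself the subject-level outcome, so the plan as written does not specify the sound version.

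Other parts of the reply stand and limit the point:

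- The formula in 9.3 is per day, and on that scale the standard error is only mildly conservative (0.034 against 0.031; type I error 0.037). The larger distortion needs rescaling to the endpoint's unit together with a model-based SE. In the unadjusted two-group model a sandwich SE was practically the same in every unit (0.0302–0.0303), but the plan names none, and it would not restore exposure weighting.
- A reader might infer that the model necessarily dilutes the bundle's effect. The documents do not support that: they do not say how the effect varies with length of ventilation, and a constant effect gives no dilution.
- A reader might infer that short-stay patients dominate the result. In the day-3 simulation, those ventilated two days or less are 34% of patients and 10% of ventilated days. They are over-represented relative to exposure, but a minority.
- A reader might extend the criticism to the time series. Its monthly average could equally be pooled DOT over ventilated days, so that wording needs clarifying and is not a demonstrated error.

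**Conclusion.** The point holds in limited form, and its severity is minor to moderate. As written, 9.3 applies a count model to a ratio and discards exposure.

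The unit dependence of model-based inference and the equal weighting of patients with the same covariates follow from algebra. Their size rests on assumed inputs: SE about 0.034 per day against 0.045 per 1000 days, and rate ratio 0.93 against 0.88 if the effect starts on day 3, with no difference if it is constant. An effect on backwards selection is expected if selection uses model-based p-values, but it was not simulated.

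The analysis is exploratory and concerns a secondary outcome. A reader might infer that the trial's main conclusions are at risk; they are not, because the 9.2 comparisons and the primary safety endpoints do not use this model.

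**What to change.** In 9.3:

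- Make each patient's DOT count while ventilated the response, with log(ventilated days) as an offset.
- Fit by quasi-Poisson with robust standard errors, so that the adjusted estimate corresponds to the pooled endpoint in section 4. Negative binomial with the same offset is acceptable and removes the unit dependence, but the text should acknowledge that it only partly closes the gap to that endpoint.
- Name the variance estimator, and use it in the backwards selection as well.
- As a clarification, define the monthly time-series rate as total DOT divided by total ventilated days in that month.

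The cost is a few sentences of SAP wording. Both quantities are already needed to form the ratio, so no new data are required.

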2.2 STUDY BACKGROUND

Antibiotic overuse is an increasingly recognized problem in intensive care units (ICUs).^{9,14} A recent multinational point-prevalence study of 1150 ICUs determined that 70% of patients surveyed were receiving antibiotics; only 54% of these patients had suspected or proven infection and only 35% had positive microbiologic cultures supporting a definitive diagnosis of infection.¹⁵ Excess antibiotic use catalyzes the acquisition and spread of multidrug-resistant organisms (MDROs), which have risen precipitously within ICUs in recent decades and are associated with excess morbidity, mortality, and healthcare expense.¹⁶⁻²³ Antibiotic overuse is also associated with adverse patient outcomes, including *Clostridioides difficile* infection, drug toxicity, and incident sepsis, as well as increases in healthcare costs and length of stay.²⁴⁻²⁸

Treatment for suspected respiratory infection—in particular, ventilator-associated pneumonia (VAP)—accounts for 50-70% of antibiotic use within ICUs.⁶⁻⁹ **Multidisciplinary case review and autopsy studies demonstrate that a substantial number of ICU patients treated for VAP are misdiagnosed, resulting in significant antimicrobial overuse.**^{10-13,29,30} For example, a multidisciplinary review of 231 cases diagnosed and treated as VAP in 6 ICUs at Johns Hopkins Hospital determined that antibiotics were not indicated in 59% of cases at the time of diagnosis, resulting in 1,183 days of unnecessary antibiotic use over 1 year.¹⁰ A similar multidisciplinary review of surgical ICUs at Johns Hopkins Hospital found that fewer than 25% of patients empirically treated for postoperative VAP met standardized criteria for infection, accounting for 1,460 days of inappropriate antibiotic therapy over 1 year.¹¹ At Michigan Medicine University Hospital, a review of patients with positive respiratory cultures who were treated for nosocomial pneumonia determined that 34% were misdiagnosed, account for a median of 12 excess days of unnecessary antibiotics per patient.³⁰

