9.4 OTHER ANALYSES

9.4.1 Safety Analyses

This study will utilize a Data and Safety Monitoring Board (DSMB) comprised of study personnel (the study PI, biostatistician, and ICU medical directors, [name]), as well as an independent medical monitor ([name], Chief of Division of Allergy, Immunology and Infectious Diseases at Robert Wood Johnson University Hospital). [name] has served on data safety and monitoring committees for multiple federally- and industry-funded clinical trials, many of which have involved the study of ventilator-associated pneumonia.

The DSMB will meet every two months to review the following safety metrics: 1) Mortality per 1000 mechanically-ventilated patient days per ICU, Ventilator- associated events (using Centers for Disease Control/National Healthcare Safety Network definitions) per 1000 mechanically-ventilated patient days per ICU, Median duration of mechanical ventilation per patient per ICU. All safety outcomes will be compared to preintervention ICU data collected over the last 5 years to ensure that postintervention values fall within 2 standard deviations of preintervention controls. The study will be halted if any safety outcome is increased by more than 2 standard deviations relative preintervention control data. If safety outcomes are decreased by more than 2 standard deviations relative to preintervention control data (i.e. in a favorable direction following the intervention), the study intervention will be continued as this is a single-arm study trial design.

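### The antibiotic-use rate is divided by ventilated days, which the bundle could change, and no companion measure is independent of ventilation

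*Combined protocol and SAP*

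**What the plan says.** Antibiotic use appears in four places in the combined protocol and SAP, in three phrasings.

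- Section 4 (Objectives and Endpoints), total use: "Total ICU antibiotic utilization rates (total antibiotic days of therapy per 1000 mechanically-ventilated patient days".
- Section 1.1 (Synopsis), broad-spectrum use: "Broad-spectrum ICU antibiotic utilization rates (broad-spectrum antibiotic days of therapy per 1000 mechanically-ventilated patient days".
- Section 9.3, interrupted time series: "Each month will have an average antibiotic DOT per mechanically-ventilated patient per day".
- Section 9.3, subject-level negative binomial model, introduced as an example: "total antibiotic DOTs on mechanical ventilation divided by total number of person days on mechanical ventilation".

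The endpoint entries fix the denominator. They do not say whether antibiotic days before intubation or after extubation belong in the numerator. Only the last definition limits the numerator to ventilated time.

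The denominator is closely tied to a primary safety endpoint, "Median duration of mechanical ventilation per patient" (section 1.1). The only local figure for the length of unnecessary treatment is in section 2.2: misdiagnosed patients "account for a median of 12 excess days of unnecessary antibiotics per patient". Section 9.1.2 makes a reduction in the ICU antibiotic rate a secondary hypothesis.

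**The concern.** A rate is a sound summary of drug exposure when the intervention leaves its denominator alone. Here that cannot be assumed. Section 3.1.1 names missed diagnosis and late effective therapy as the main risks, and either could lengthen ventilation. Fewer unnecessary courses could equally shorten it. In both cases the rate changes for reasons unrelated to how much antibiotic patients received.

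Under the section 9.3 definition, counting also stops at extubation. A course averted by the bundle is credited only for its ventilated part. A course prolonged because a culture result was held back is charged only for that part.

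What is at stake is the secondary conclusion on antibiotic use, and the preliminary efficacy data that the pilot is meant to supply. The primary safety comparison does not depend on this rate.

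**Working it through.** The plan states no expected antibiotic rate, ventilation duration or sample size, so there is no figure of its own to reproduce. The 12-day course length comes from section 2.2. Every ventilation duration, the 7-day course and the 800 per 1000 baseline are assumptions.

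**1. Denominator alone.** If antibiotic days stay fixed and ventilated days rise by a fraction x, the relative change in the rate is 1/(1+x) − 1.

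- x = 0.05: −4.8%
- x = 0.10: −9.1%
- x = 0.20: −16.7%

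The reverse also holds: 10% fewer ventilated days give 1/0.90 − 1 = +11.1%, so faster extubation would look like heavier use.

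**2. Extra days that carry some antibiotic.** Take 800 antibiotic days per 1000 ventilated days and add 100 ventilated days (10%), each carrying r antibiotic days. The new rate per 1000 is (800 + 100r)/1.1.

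| r | Rate per 1000 |
|---|---|
| 0 | 727 |
| 0.4 | 764 |
| 0.8 | 800 |
| 1.2 | 836 |

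The rate falls when the added days carry less antibiotic than the average of 0.8 and rises when they carry more.

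**3. One patient under the section 9.3 definition.** Assume a single agent started after 3 ventilated days and given for 7 days. With D ventilated days, the counted days are min(7, D − 3) and the rate is 1000 × min(7, D − 3)/D.

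| D | Counted days | Rate per 1000 |
|---|---|---|
| 6 | 3 | 500 |
| 10 | 7 | 700 |
| 12 | 7 | 583 |
| 16 | 7 | 438 |

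The patient receives 7 antibiotic days in every row. The rate climbs until the course ends on the ventilator. From D = 10 to D = 16 it then falls by 38% with nothing avoided.

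**4. Part of a course that is counted.** With V ventilated days left when a 12-day course starts, the share counted under the section 9.3 definition is min(V, 12)/12.

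- V = 3: 25%
- V = 6: 50%
- V = 10: 83%
- V = 12 or more: 100%

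If remaining ventilation is exponential with mean m, the expected share is m(1 − exp(−12/m))/12: 32%, 48% and 58% for m = 4, 7 and 10 days.

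**5. The other reading of the numerator.** If the secondary endpoints count all antibiotic days in the ICU, use after extubation but before ICU discharge is included, and only later use is lost. The numerator and denominator then cover different time. If extubation is later within an unchanged ICU stay, the antibiotic days are already in the numerator, so the step 1 reductions apply in full even if the added ventilated days carry antibiotics.

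**The case against.** **The restricted numerator is only an example.** It is explicit only in an exploratory model, and the endpoints are labelled as ICU use. This stands. A reader might infer that every antibiotic endpoint stops at extubation, but the documents do not say so. For the secondary endpoints the fault is an undefined numerator window plus the ventilated-day denominator.

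**The loss may be small.** A reader might infer that most of an unnecessary course goes uncounted. The documents give neither ventilation durations nor times from culture to extubation, and step 4 runs from 25% to 100%. The 12-day median also comes from patients treated for nosocomial pneumonia, a group not limited to ventilated patients. This stands: the loss is possible but cannot be sized.

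**The bias has no fixed direction.** This stands, as steps 2 and 3 show. Because the same definition applies before and after implementation, uncounted savings understate the effect. Uncounted increases overstate it, and so does dilution by ventilated days with little antibiotic.

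**Ventilation duration is reported anyway.** It is a primary endpoint, reviewed every two months, with the provision that "The study will be halted if any safety outcome is increased by more than 2 standard deviations relative preintervention control data" (section 9.4.1). Readers would see a large shift. But the endpoint is a median, whereas the rate's denominator is a sum of days: long-stay patients can add many days while the median stays put. Nor does a separate median correct the rate. The subject-level model does not help either, because its outcome is this same rate.

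**The stated objective is ICU use, in a pilot.** This is fair. It argues for keeping the rate and adding a sensitivity measure, not for replacing the endpoint.

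**A fixed window has faults too.** A window ending on day 14 would cut a 12-day course started on day 5 to 10 days, and one started on day 8 to 7 days. Early deaths would lower the count. Both points stand and shape the fix.

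**Conclusion.** The point holds in limited form and should be addressed. Followed exactly, the plan could show a lower antibiotic rate with no antibiotic avoided, or a higher one with none added. No planned measure would separate these from a real change in use. With antibiotic days unchanged, the reduction is 4.8% to 16.7% for 5% to 20% more ventilated days. That range assumes the added days contribute no further antibiotic days to the numerator; otherwise the fall is smaller or becomes a rise.

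A reader might go further and infer that longer ventilation will be mistaken for an antibiotic benefit. The documents support this only as one possible outcome: they give no evidence that the bundle lengthens ventilation, and the effect can run either way. The loss after extubation is certain in kind under the section 9.3 definition, but unknown in amount.

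**What to change.** 1. Keep the rate per 1000 ventilated days. State one numerator window, and use it in sections 1.1, 4 and 9.3, including the time series.
2. Add a prespecified sensitivity measure: total and broad-spectrum antibiotic days per patient over a window that does not depend on ventilation, such as a fixed number of days from the first ventilated day. It should be long enough to contain courses that start later. For example, a 12-day course begun on day 8 ends on day 8 + 12 − 1 = 19.
3. State how death is handled: report deaths alongside, or use antibiotic days per day alive in the window.
4. Interpret the rate together with this measure, ventilation duration and mortality, and report any disagreement in direction. The measure should inform the conclusion and not act as a strict gate.

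The cost is analysis-plan wording and a longer extraction, assumed to be available from the same electronic record for both the intervention year and the five-year control period; the documents do not describe extraction after ICU discharge. The downside is that some ward antibiotic days not directed by the ICU team will be included.
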